6.5 Criteria for Removal from Study

Treatment may continue until one of the following criteria applies:

- Disease progression,
- Intercurrent illness that prevents further administration of treatment,
- Unacceptable adverse event(s),
- Patient decides to withdraw from the study,
- General or specific changes in the patient's condition render the patient unacceptable for further treatment in the judgment of the investigator, or
- Treatment delays of > 2 weeks due to adverse events.

Treatment may be interrupted within a cycle for up to 2 weeks and missed doses should be omitted. However, patients will be replaced if they do not receive at least 80% of the planned treatment in the first cycle of therapy.

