- 3.1.11 Patients with childbearing potential, including any female who has had a negative serum pregnancy test within 2 weeks prior to the first dose of study treatment, preferably as close to the first dose as possible, and agrees to use adequate contraception. GSK acceptable contraceptive methods, when used consistently and in accordance with both the product label and the instructions of the physician, are as follows: (1) complete

abstinence from sexual intercourse for 14 days before exposure to investigational product, through the dosing period, and for at least 21 days after the last dose of investigational product, (2) oral contraceptive, either combined or progestogen alone, (3) injectable progestogen, implants of levonorgestrel, estrogenic vaginal ring, percutaneous contraceptive patches, intrauterine device (IUD) or intrauterine system (IUS) with a documented failure rate of less than 1% per year, (4) male partner sterilization (vasectomy with documentation of azoospermia) prior to the female subject's entry into the study, and this male is the sole partner for that subject, (6) double barrier method: condom and an occlusive cap (diaphragm or cervical/vault caps) with a vaginal spermicidal agent (foam/gel/film/cream/suppository) Female subjects who are lactating should discontinue nursing prior to the first dose of study drug and should refrain from nursing throughout the treatment period and for 14 days following the last dose of study drug.

3.1.12 Adequate organ system function as defined in Table 1

Table 1. Definitions for Adequate Organ Function

System	Laboratory Values
Absolute neutrophil count (ANC)	$\geq 1.5 \times 10^9/L$
Hemoglobin	$\geq 9 \text{ g/dL (5.6 mmol/L)}$
Platelets	$\geq 100 \times 10^9/L$
Prothrombin time (PT) or international normalized ratio (INR) ^a	$\leq 1.2 \times \text{ULN}$
Activated partial thromboplastin time (aPTT)	$\leq 1.2 \times \text{ULN}$
Total bilirubin	$\leq 1.5 \times \text{ULN}$
Alanine amino transferase (ALT) and Aspartate aminotransferase (AST) ^b	$\leq 2.5 \times \text{ULN}$
Serum creatinine	$\leq 2.0 \text{ mg/dL (133 } \mu\text{mol/L)}$
Or, if $>2.0 \text{ mg/dL}$: Calculated creatinine clearance (ClCR) by Cockroft-Gault formula	$\geq 30 \text{ mL/min}$
Urine Protein to Creatinine Ratio (UPC; appropriate appendix) ^c	<1

- a. Subjects receiving anticoagulant therapy are eligible if their INR is stable and within the recommended range for the desired level of anticoagulation.

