- b. Concomitant elevations in bilirubin and AST/ALT above 1.0 x ULN (upper limit of normal) are not permitted.
- c. If UPC ≥ 1 , then a 24-hour urine protein must be assessed. Subjects must have a 24-hour urine protein value $<1 \text{ g}$ to be eligible.

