6.1.2 Criteria for Starting Subsequent Cycles

A cycle may be repeated every 28 days (+/- 3 days) if the patient has at least stable disease and continue to meet laboratory parameters as defined in the eligibility section.

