7.0 Dose Delays/Modifications for Adverse Events

Recommendations for investigational product (IP) dose interruptions/modifications in case of specific treatment-emergent AEs are provided in the following sections.

As a general rule, if dose reduction of IP is necessary, the dose should be reduced stepwise by 200 mg at each step, and the subject should be monitored for 10 to 14 days at each dose level. If toxicity does not abate during this monitoring time, the IP may need to be interrupted and/or the dose further decreased with continued monitoring for an additional 10-14 days at each dose level, and so on.

If the toxicity has abated with reduction of the dose and dose re-escalation is considered safe by the investigator, the IP dose can then be increased step-wise back to the pre-event dose (in 200 mg increments, after monitoring for 10-14 days at each dose level to ensure that toxicity did not recur or worsen).

If a subject's treatment has been interrupted for more than 21 days, the Investigator must contact the GSK Study Physician to review the subject's condition in order to resume the treatment.

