7.2 Dose Interruptions/Modifications for Hepatotoxicity

Recommendations for investigational product dose interruptions/modifications in case of liver-related treatment-emergent AEs are provided in Table 3. As a general rule, since many subjects are taking multiple concurrent medications, it is critical to (a) do a thorough evaluation of the subject's concurrent medications, and (b) identify and discontinue those with known hepatotoxicity and replace with a non-hepatotoxic equivalent for the same indication if necessary.

Table 3. Dose modifications for hepatotoxicity.

Event	Dose Modification Algorithms
(A). ALT of \leq 3.0 x upper limit of normal (ULN)	Continue IP at current dose with full panel liver function tests (LFTs) ^a monitored as per protocol.
(B). ALT $>$ 3.0 x ULN to \leq 8.0 x ULN without bilirubin elevation (defined as total bilirubin $<$ 2.0 x ULN or direct bilirubin \leq 35%) and without hypersensitivity symptoms (e.g., fever, rash)	
 1. Continue IP at current dose. 2. Perform the following assessments for excluding hypersensitivity and other contributing factors: 
 • Eosinophil count • Viral serology for hepatitis A, B and C • Liver imaging 3. Monitor subject closely for clinical signs and symptoms; perform full panel LFTs weekly or more frequently if clinically indicated until alanine

Event	Dose Modification Algorithms

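### Sections 6.5 and 6.1.2 conflict with Section 7 on how long an adverse-event hold may last and on which liver values allow dosing into a new cycle, and nothing says which section governs

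*Combined protocol and SAP*

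**What the plan says.** **Length of a hold.** Section 6.5 lets treatment run until one of several criteria applies, one of which is "Treatment delays of > 2 weeks due to adverse events". It then adds: "Treatment may be interrupted within a cycle for up to 2 weeks and missed doses should be omitted". Section 7.0, whose heading concerns dose delays and modifications for adverse events, provides that if a patient's "treatment has been interrupted for more than 21 days, the Investigator must contact the GSK Study Physician to review" the patient's "condition in order to resume the treatment".

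**Laboratory values at a cycle start.** Section 6.1.2 allows a cycle to be repeated every 28 days (+/- 3) if the patient has at least stable disease and would "continue to meet laboratory parameters as defined in the eligibility section". Those limits are in Table 1 under Section 3.1.12: ALT and AST at most 2.5 x ULN, total bilirubin at most 1.5 x ULN, and UPC below 1 (or 24-hour protein below 1 g). Footnote b adds: "Concomitant elevations in bilirubin and AST/ALT above 1.0 x ULN (upper limit of normal) are not permitted".

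Section 7.2, Table 3, gives dosing instructions by liver value:
- Row A (ALT up to 3.0 x ULN): "Continue IP at current dose with full panel liver function tests". It carries no bilirubin condition.
- Row B (ALT above 3.0 and up to 8.0 x ULN, no hypersensitivity symptoms, and total bilirubin below 2.0 x ULN or a direct fraction of at most 35%): the current dose continues, with a work-up and at least weekly liver tests.
- Isolated bilirubin rise: no dose change is required. Above 2 x ULN, bilirubin is fractionated, and the same dose continues if it is mainly indirect.

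Section 7.1 interrupts drug at UPC 3 or more and restarts it, reduced by 200 mg, once UPC is below 3.

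**The concern.** For the same hold or the same laboratory value, one section ends or withholds drug and another resumes or continues it. If 6.1.2 is followed, drug is withheld for an indirect bilirubin rise that Table 3 itself explains can occur without liver injury. If Table 3 is followed, a patient with ALT of 8 x ULN can start a cycle outside 6.1.2. Section 13.2.1 sets a no-deviations rule and 13.2.2 sends unplanned deviations to the DSMB, so obeying one section may be reportable under the other.

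The two conflicts can also compound. An ALT of 5 x ULN at a cycle start may continue under row B but blocks the cycle under 6.1.2. If that block outlasts 2 weeks, 6.5 ends treatment. At stake are patient safety, consistent handling between patients and over time, and the counts of discontinuations and deviations.

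**Working it through.** The plan states no figure to reproduce. The check sets the rules side by side.

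**Hold length** (6.5 against 7.0), with 2 weeks = 14 days; the two limits differ by 21 - 14 = 7 days.

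| Adverse-event hold | Section 6.5 | Section 7.0 | Result |
|---|---|---|---|
| up to 14 days | allowed | no special step | agree |
| 15 to 21 days | ends treatment | silent | no direct conflict |
| over 21 days | ends treatment | may resume after contact | contradiction |

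Under 6.5 a patient held for more than 21 days because of an adverse event is already off treatment, so the 7.0 provision has nothing to act on.

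**Laboratory values at a cycle start** (6.1.2 with eligibility Table 1, against Section 7).

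| Value | 6.1.2 | Section 7 | Ratio of Section 7 ceiling to 6.1.2 limit |
|---|---|---|---|
| ALT above 2.5, up to 3.0 x ULN | no new cycle | row A: continue | 3.0 / 2.5 = 1.2 |
| ALT above 3.0, up to 8.0 x ULN, row B conditions met | no new cycle | row B: continue, monitored | 8.0 / 2.5 = 3.2 |
| ALT and bilirubin both above 1.0 x ULN | no new cycle (footnote b) | row A, or row B if its bilirubin condition is met: continue | row B total bilirubin 2.0 / 1.5 = 1.33; no ceiling if direct fraction is at most 35% |
| Isolated, mainly indirect bilirubin above 1.5 x ULN | no new cycle | same dose | no upper limit stated |
| UPC 1 to below 3 with 24-hour protein of 1 g or more | no new cycle | restart after a hold, reduced dose | 3 / 1 = 3 |

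The last row is a conflict only when the restart coincides with a cycle start.

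Section 6.2 schedules hepatic tests at weeks 4 and 8, so these values will be in hand when the 6.1.2 check is made. Row B monitors until ALT/AST fall to Grade 1 and does not stop at the cycle boundary, so it cannot simply be read as a within-cycle rule.

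**Does anything rank the sections?** Section 6.2 refers only UPC of 3 or more to the dose-modification table. Study Calendar footnote a makes an exception for toxicity adjustments without naming a governing section. Section 13.2.3 makes the DSMB arbiter when people dispute whether a treatment deviates. None of these sets an order of precedence.

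**The case against.** The best defence is that Section 7 calls its content recommendations and a general rule, so 6.5 and 6.1.2 are the firm limits and the stricter one applies. That is workable, but the plan does not say it. The 21-day provision is phrased as an obligation, and on this reading it would be dead text. The Table 3 instructions to continue would also lapse at each cycle start without saying so.

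A second defence separates a delay (6.5) from an interruption (7.0). It fails because 6.5 caps both at 2 weeks. One could add the two allowances, 14 + 14 = 28 days, to make room for a hold over 21 days, but nothing in 6.5 says the count restarts at a cycle boundary.

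Third, 13.2.3 offers a remedy. It does, case by case and after the event.

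Several stronger readings are tempting but not supported:
- *Holds of 15 to 21 days are contradictory.* Section 7.0 is silent there; requiring no contact is not an instruction to resume.
- *Every UPC from 1 to below 3 conflicts.* No row says to continue in that range; the row covers only restarting after a hold.
- *Platelets conflict too.* Section 7.1 continues at Grade 1 or 2, but the documents print no platelet cut-offs for those grades.
- *Haemoglobin conflicts.* Section 7.1 states only that anaemia without bleeding has no specific dose-reduction rule; 6.1.2 still bars a new cycle below 9 g/dL.
- *A Section 7 instruction to continue can last at most 28 + 3 = 31 days.* Section 6.2 moves hepatic and chemistry tests to every 8 weeks after 6 months, while calendar footnote c repeats assessments every 28 days, so that maximum is not established.
- *Table 3 is unsafe.* Row B requires an eosinophil count, viral serology, liver imaging and close monitoring. Row C re-challenge needs company approval and fresh consent.

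**Conclusion.** Two contradictions stand in the current text: adverse-event holds over 21 days, and liver values at a cycle start (ALT above 2.5 and up to 8.0 x ULN under the Table 3 conditions, concomitant ALT and bilirubin elevation, and isolated, mainly indirect bilirubin above 1.5 x ULN). The proteinuria restart is a smaller third case. This rests on the printed thresholds alone and needs no outside source.

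How many patients would fall in these bands is unknown: the adverse event list gives no grades, and no rate of long holds is given. The trial has one institution and one monitoring team, so the likely effect is uneven handling between patients or over time. A reader might infer an effect on the response-rate denominator or on scan timing; this comparison of dosing rules does not establish either. The point should be fixed because opposite dosing instructions for the same patient can be removed by wording.

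**What to change.** **Hold length.** Put one maximum adverse-event hold and one resumption rule, in the same words, in 6.5 and 7.0, counted continuously across cycle boundaries. The default is to keep 14 days and delete the 21-day sentence. If the clinical team prefers 21 days, change both limits in 6.5 and allow later resumption only with company study physician approval. State that the limit also applies to the row C and proteinuria holds, whose rows give no maximum of their own.

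**Cycle start.** Keep the eligibility limits in 6.1.2 for ANC, haemoglobin, platelets, PT/INR, aPTT and creatinine or creatinine clearance, and for AST when it rises on its own (ALT within the eligibility limit). Add one exception: for ALT with any accompanying AST rise, bilirubin and proteinuria, the Section 7 tables decide whether dosing continues at a cycle start.

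Do not replace the whole 6.1.2 laboratory condition with the Section 7 tables. ANC, coagulation and creatinine have no named row in Section 7, and Table 3 is keyed to ALT with no AST threshold for changing the dose, so those limits would be lost. With the narrower exception, no separate haemoglobin line is needed.

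**Cost.** Amendment wording only, with no added patients or procedures. The small downside is that some patients will start cycles at liver values above the eligibility limits, under Table 3 monitoring.

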6.6 Supportive Care and Other Concomitant Therapy

6.6.1 Investigational Therapy

No other investigational treatment may be given while the patient is on study.

6.6.2 Supportive Care

Appropriate antibiotics, blood products, antiemetics, fluids, electrolytes and general supportive care are to be used as necessary.

6.6.3 Concomitant Medications

Permitted Medications

All subjects will be asked to provide a complete list of prescription and over-the-counter medications that have been taken within the previous 4 weeks prior to Screening. The investigator must be informed as soon as possible about any new medication(s) taken from the time of Screening until the completion of the post-treatment follow-up visit.

All concomitant medications taken during the study will be recorded in the case report form (CRF) with indication, dose information, and dates of administration.

Subjects should receive full supportive care during the study, including transfusion of blood and blood products, treatment with antibiotics, analgesics, erythropoietin, or bisphosphonates, when appropriate.

Anti-emetics (such as prochlorperazine, lorazepam, ondansetron or other 5-HT antagonists) may be administered prophylactically in the event of nausea. Anti-diarrheals, such as loperamide, may be administered as needed in the event of diarrhea. Although acetaminophen at doses of ≤ 2 g/day is permitted, it should be used with caution in subjects with impaired liver function.

Permitted Medications – Use with Caution

Specific recommendations regarding anticoagulants:

Results from drug-drug interaction studies conducted in subjects with cancer suggest that pazopanib has no effect on the metabolism of S-warfarin. Hemorrhagic events, however, have been reported in clinical studies with pazopanib; therefore, pazopanib should be used with caution in subjects with increased risk of severe bleeding or who are receiving concomitant anticoagulant therapy (e.g., warfarin or its derivatives, low molecular weight heparin, unfractionated heparin). Subjects taking concomitant anticoagulant therapy should be monitored regularly for changes in relevant coagulation parameters as clinically indicated, as well as for any clinical bleeding episodes.

Specific recommendations regarding hypoglycemic therapy including insulin:

Results from drug-drug interaction studies conducted in subjects with cancer suggest that there will be no clinically relevant pharmacokinetic interaction between pazopanib and hypoglycemic agents. Transient decreases in serum glucose (mainly Grade 1 and 2, rarely Grade 3) have been observed in clinical studies with pazopanib. In addition, decreases in blood sugar have been recently reported in subjects treated with another small molecule tyrosine kinase inhibitor, sunitinib (British Journal of Cancer 2008: 99, 1380). Such changes may require an adjustment in the dose of hypoglycemic and/or insulin therapy. Subjects should be advised to report symptoms of hypoglycemia (e.g., confusion, visual disturbances, palpitations, sweating). Serum glucose should be tested during treatment with pazopanib as outlined in the protocol and as clinically indicated.

The Effects of Pazopanib on Other Drugs

In vitro data indicate that pazopanib is a potential inhibitor for CYP3A4, CYP2C8, CYP2D6, CYP1A2, CYP2C9, CYP2C19, CYP2A6, CYP2B6, and CYP2E1. Pregnen X receptor transient transfection assay suggested some potential for human CYP3A4 induction at high concentrations. Results from drug-drug interaction studies conducted in subjects with cancer suggest that pazopanib is an inhibitor of CYP3A4, CYP2C8, and CYP2D6 *in vivo*, but had no clinically relevant effect on CYP1A2, CYP2C9 or CYP2C19 metabolism. Therefore, concomitant use of pazopanib with agents with narrow therapeutic windows that are metabolized by CYP3A4, CYP2D6, or CYP2C8 is not recommended. Coadministration may result in inhibition of the metabolism of these products and create the potential for serious adverse events. In addition, the potential for drug interaction with such medications, although diminished, may persist after the last dose of pazopanib due to its long half-life (i.e., mean 30.9 hours); therefore, continue to exercise **CAUTION** for at least 7 days and up to 15 days after the last dose of pazopanib when administering these medications. These medications include (but are not limited to):

- Ergot derivatives: dihydroergotamine, ergonovine, ergotamine, methylergonovine (potential increased risk for developing ergot toxicity that includes severe vasospasm leading to peripheral as well as cerebral ischemia)
- Neuroleptics: pimozide (potential increased risk for QT interval prolongation, ventricular arrhythmia, and sudden death)
- Antiarrhythmics: bepridil, flecainide, lidocaine, mexiletine, amiodarone, quinidine, propafenone (potential increased risk for QT interval prolongation and Torsade de Pointes)

- Immune modulators: cyclosporine, tacrolimus, sirolimus (potential increased risk for nephrotoxicity and neurotoxicity)
- Miscellaneous: quetiapine, risperidone, clozapine, atomoxetine.

The Effects of Other Drugs on Pazopanib

Results from *in vitro* studies suggest that the oxidative metabolism of pazopanib in human liver microsomes is mediated primarily by CYP3A4, with minor contributions from CYP1A2 and CYP2C8. Furthermore, *in vitro* data suggest that pazopanib is a substrate for p-glycoprotein. Substances that induce or inhibit CYP3A4 may alter the pharmacologic effects of pazopanib and should be used with **CAUTION**.

Medications that inhibit CYP3A4 may result in increased plasma pazopanib concentrations. Co-administration of strong CYP3A4 inhibitors is prohibited (see Section on Prohibited Medications); therefore selection of an alternate concomitant medication with no or minimal potential to inhibit CYP3A4 is recommended.

CYP3A4 inducers may decrease plasma pazopanib concentrations. Selection of an alternate concomitant medication with no or minimal enzyme induction potential is recommended. **Drugs that induce CYP3A4 and may decrease pazopanib plasma concentrations include (but are not limited to):**

- Glucocorticoids: cortisone (>50 mg), hydrocortisone (>40 mg), prednisone (>10 mg), methylprednisolone (>8 mg), dexamethasone (>1.5 mg)
- Anticonvulsants: phenytoin, carbamezepine, phenobarbital, oxcarbazepine
- HIV antivirals: efavirenz, nevirapine
- Antibiotics: rifampin (rifampicin), rifabutin, rifapentine
- Miscellaneous: St. John's Wort, modafinil, pioglitazone, troglitazone

Prohibited Medications

Subjects should not receive other anti-cancer therapy [cytotoxic, biologic, radiation, or hormonal (other than leuprolide or other GnRH agonists)] while on treatment in this study.

Medications that inhibit CYP3A4 may result in increased plasma pazopanib concentrations; therefore, co-administration of strong CYP3A4 inhibitors is **PROHIBITED** beginning **14** days prior to the first dose of study drug until discontinuation from the study. **Strong CYP3A4 inhibitors include (but are not limited to):**

- Antibiotics: clarithromycin, telithromycin, troleandomycin

- HIV: protease inhibitors (ritonavir, indinavir, saquinavir, nelfinavir, amprenavir, lopinavir)
- Antifungals: itraconzaole, ketoconazole, voriconazole, fluconazole
- Antidepressants: nefazodone

6.6.4 Other Treatments Allowed on Study

Surgery and radiation therapy are not permitted while the patient is on the current study.

7.0 Dose Delays/Modifications for Adverse Events

Recommendations for investigational product (IP) dose interruptions/modifications in case of specific treatment-emergent AEs are provided in the following sections.

As a general rule, if dose reduction of IP is necessary, the dose should be reduced stepwise by 200 mg at each step, and the subject should be monitored for 10 to 14 days at each dose level. If toxicity does not abate during this monitoring time, the IP may need to be interrupted and/or the dose further decreased with continued monitoring for an additional 10-14 days at each dose level, and so on.

If the toxicity has abated with reduction of the dose and dose re-escalation is considered safe by the investigator, the IP dose can then be increased step-wise back to the pre-event dose (in 200 mg increments, after monitoring for 10-14 days at each dose level to ensure that toxicity did not recur or worsen).

If a subject's treatment has been interrupted for more than 21 days, the Investigator must contact the GSK Study Physician to review the subject's condition in order to resume the treatment.

